4.3 VRC01LS: VRC-HIVMAB080-00-AB

VRC01LS is a broadly neutralizing human MAb targeted against the HIV-1 CD4 binding site. It was developed by VRC/NIAID/NIH.

VRC01 was modified by site-directed mutagenesis to increase its binding affinity for the neonatal Fc receptor (FcRn); the resulting antibody is designated VRC01LS. The LS designation specifies methionine to leucine (L) and asparagine to serine (S) (M428L/N434S, referred to as LS) changes within the C-terminus of the heavy chain constant region far outside of the antigen-combining site (53). The VRC01LS is an IgG1, and the glycosylation pattern is derived from its production in a Chinese Hamster Ovary (CHO) mammalian cell line.

While the LS mutation confers enhanced FcRn binding capability to the bNAb and allows its efficient transport to and accumulation in mucosal compartments, VRC01LS displays normal binding to other FcRs, such as Fc γ RIIIa, thus not impeding ADCC activity. The VRC01LS variant also retains comparable neutralization breadth and potency to wild-type (WT) VRC01. In Indian rhesus macaques, the LS mutant exhibited a 2.5-fold longer half-life (VRC01, 4.65 days; VRC01-LS, 11.80 days) and a 2.5-fold slower clearance rate than the wild type mAb (VRC01, 16.52 ml day⁻¹ kg⁻¹; VRC01-LS, 6.47 ml day⁻¹ kg⁻¹). The LS variant also persisted in rectal mucosal tissues for more than 70 days whereas the VRC01 (WT) antibody was undetectable at day 28 (49).

The bulk lot of the drug substance was manufactured under cGMP using a stably transfected CHO cell line, purified, and the drug product vials were filled and labeled at the VRC, Vaccine Clinical Material Program operated by Leidos Biomedical Research, Inc., Frederick, MD. Each product vial contains 6.25 mL volume at a concentration of 100 mg/mL VRC01LS in formulation buffer containing 25 mM Sodium Citrate, 50 mM Sodium Chloride, and 150 mM L-Arginine Hydrochloride at pH 5.8.

Details on VRC01LS composition and manufacturing can be found in the IB.

4.4 Trial design rationale

Two large scale phase 2b efficacy studies of VRC01 opened in parallel in 2016. HVTN 703/HPTN 081 enrolled the first participant on May 17, 2016, and will enroll 1900 participants at risk of contracting HIV-1 infection in Sub Saharan Africa; whereas HVTN 704/HPTN 085 will enroll 2700 participants at risk of contracting HIV-1 infection in the Americas and Switzerland. HVTN 704/HPTN 085 opened for accrual on March 31st 2016, and the first participant was enrolled on April 6th 2016. Both studies will evaluate the ability of two different IV doses (10 mg/kg and 30 mg/kg, administered every 8 weeks) of VRC01 to prevent HIV-1 infection. Since the target populations for HVTN 703/HPTN 081 and HVTN 704/HPTN 085 predominantly acquire HIV-1 infection through sexual exposure, the concentration and function of Abs in the rectal and genital mucosae following systemic administration are potentially key to the effectiveness of the passive immunoprophylaxis approach. While phase 1-2a studies have collected limited samples to measure Ab levels in human mucosal secretions, there is very little data (recently generated in a Mucosal Sub-study to HVTN 104) on the Ab levels or distribution in human mucosal tissues, which serve as critical portal of entry for HIV-1 infection. Mucosal biopsies cannot be performed in the context of an efficacy trial enrolling high risk individuals because of potential alterations in risk of infection; however, HVTN 116 presents a crucial opportunity to examine the pharmacokinetic behavior and functionality of VRC01 and VRC01LS in mucosal tissues.

In parallel with HVTN 703/HPTN 081 and HVTN 704/HPTN 085, it is desirable to gather in-depth data on the distribution and persistence, as well as the

functionality of VRC01 in mucosal secretions and tissues at the dosages planned in the phase 2b trial. HVTN 116 will investigate concentrations and tissue distributions of the VRC01 antibody in mucosal tissues that are common sites of HIV exposure, and compare these to paired serum levels. HVTN 703/HPTN 081 and HVTN 704/HPTN 085 will establish serum antibody levels and correlate those with protection. However, a correlation between HIV prevention, the serum antibody levels, and the mucosal antibody levels of the VRC01 antibody cannot be established in these efficacy trials alone. HVTN 116, which includes arms that mirror the infusion schedule of HVTN 703/HPTN081 and HVTN 704/HPTN 085, can bridge the gap from serum to mucosal levels and therefore help us in understanding the underlying biological tenets of Antibody Mediated Protection (AMP), particularly with respect to mucosal challenge. Furthermore, HVTN 116 will give us the opportunity to investigate a novel variant, designated VRC01LS, with enhanced FcRn binding capability. HVTN 116 will therefore compare serum and mucosal pharmacokinetics and functionality of this LS variant of the antibody to the wild-type VRC01 antibody, in single- and repeated-dose regimens of 30mg/kg.

Generally, the minimum number of biopsies needed in order to conduct measurements of levels is 1 per tissue, for immunohistochemistry it is also 1 per tissue, and for the infectivity assays the numbers we propose are 3 for colon, 3 for vagina, and 2 for cervix. Due to the uneven distribution of vasculature, FcRs and immune aggregates in tissue, we expect mucosal biopsies to display increased variability in infectivity challenge assays. Therefore, replicates are essential. The necessity of replicates was illustrated by the rectal explant infections we conducted on 7 male participants after VRC01 infusions in HVTN104. Upon challenge with a VRC01 sensitive virus, 4 participants demonstrated resistance to infection in 3/3 biopsies, 2 participants showed resistance in 2/3 biopsies, and 1 showed resistance in 1/3 biopsies. Consequently, the infectivity assay will need a minimum of 2 biopsies in order to evidence any partial protection.

Congruently, two ectocervical and three vaginal biopsies are requested to lend power to our ability to measure true Ab-mediated inhibition of HIV-1 infection *ex vivo*. In pilot experiments utilizing vaginal biopsies from participants who had not received an Ab infusion, we found that 16 of 20 vaginal biopsies collected from 5 participants were infected (one participant was sampled twice; 1 participant had 0/3 biopsies infected by the challenge virus and 1 participant had 4/5 biopsies infected). Due to the immunological heterogeneity of the mucosal tissue and the small size of the biopsies, triplicate biopsies (vaginal) are needed, whenever possible, particularly when a small number of participants is recruited for each group. Multiple collection timepoints are required to answer the following questions: what concentration of VRC01 or VRC01LS reaches mucosal sites and how quickly do these levels decay? Do functional levels reach the mucosal tissues and if so, how long are they maintained?

In summary, HVTN 116 will provide additional supportive data for planned and postulated uses of VRC01 for the prevention of HIV acquisition. The primary goals are to further validate the safety of two doses and to interrogate the

distribution, persistence, and functionality of the antibody in relevant mucosal compartments. Additionally, HVTN 116 will provide safety data for the novel variant, VRC01LS, and will establish the distribution, persistence, and functionality of this Ab in mucosal tissues.

Collections will include cervicovaginal secretions as well as cervical and vaginal biopsies (as well as rectal secretions and biopsies at the Seattle site) in those born female and the collection of rectal secretions and semen as well as rectal biopsies in those born male. The proposed timepoints will provide the opportunity to establish the mucosal levels of the respective antibodies over time, as well as the functional capabilities at peak levels and low levels.

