5.3 Exploratory objectives

Exploratory objective 1:

For each sex at birth, to evaluate the pharmacokinetics of VRC01LS in serum versus mucosa in each mucosal compartment

Exploratory objective 2:

To evaluate the levels of VRC01LS in serum, mucosal secretions, and mucosal tissues and those of VRC01 at the 30 mg/kg dose level.

Exploratory objective 3:

To evaluate the tissue distribution of VRC01/VRC01LS in mucosal biopsies.

Exploratory objective 4:

To compare the levels and functionality of VRC01/VRC01LS in mucosal secretions and tissues between the cervical, vaginal, and rectal compartments from the same participant.

Exploratory objective 5:

To assess the relationship between inflammation in mucosal biopsies and levels of antibody in these tissues and related secretions.

Exploratory objective 6:

To assess the acceptability and tolerability of repeat mucosal sampling, including secretions and biopsies, for application in future studies.

Exploratory objective 7:

To assess the relationship between Fc receptor genotypes and VRC01/VRC01LS pharmacokinetics and/or *ex vivo* infectivity of biopsies.

Exploratory objective 8:

To further evaluate the retention of functional characteristics of *in vivo*-infused VRC01/VRC01LS in each group, additional assays may be performed, including on samples from other timepoints.

Exploratory objective 9:

To conduct analyses related to furthering the understanding of HIV, immunology, vaccines, antibody mediated prevention, and clinical trial conduct.

6 Statistical considerations

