9.6 Mucosal sampling

Mucosal secretion and biopsy samples will be collected at the timepoints indicated in [Appendix L](#), [Appendix M](#), [Appendix N](#), and [Appendix O](#). All participants in this trial will have consented to mucosal specimen collections. Participants born male will provide semen, rectal fluids, and rectal biopsies. Participants born female will provide cervicovaginal fluids, as well as cervical and vaginal biopsies. At the Seattle CRS, female participants will also provide rectal fluids and rectal biopsies, if they agree to do so. Small (~2-4 mm) tissue biopsies are obtained from the vagina and cervix using a speculum and from the rectum by anoscopy by experienced clinicians. The number of biopsies per mucosal compartment and visit is described in detail in [Table 9-1](#) and [Table 9-2](#), and also outlined in [Appendix H](#), [Appendix I](#), [Appendix J](#), and [Appendix K](#), however fewer samples may be taken based on the judgment of the performing clinician. If a female participant is no longer willing to provide cervicovaginal specimens, a switch to the rectal compartment is possible. During the trial, a participant may decline all or some of the mucosal biopsies or secretion collections, but they should be encouraged to continue with any collections that they deem acceptable until the end of the trial.

Table 9-1 Mucosal biopsy collection schedule for Groups 1-3

Tissue	Function	Visit 2 (Baseline)	Visit 14 (Month 6)	Visit 15 (Month 7)	Visit 16 (Month 9)	Visit 17 (Month 12)	Visit 18** (Month 15)	Visit 19** (Month 18)
Rectal # of Bx and Use	Ab levels	1	1	1	1	1	1	1
	IHC	1	1	1	1	1	1	1
	Infectivity	3	3	3	3	3	3	3
	Total = 35*/25	5	5	5	5	5	5	5
Ectocervical # of Bx and Use	Ab levels	1	1	1	1	1	1	(1)***
	IHC	1	1	1	1	1	1	(1)***
	Infectivity	2	2	-	-	-	-	-
	Total = 16*/14	4	4	2	2	2	2	(2)***
Vaginal # of Bx and Use	Ab levels	1	1	1	1	1	1	(1)***
	IHC	1	1	1	1	1	1	(1)***
	Infectivity	3	3	3	3	(3)***	(2-3)***	(2-3)***
	Total = 24*/22	5	5	5	5	2 [(5)***]	2 [(4-5)***]	(2-5)***

* Number of samples refers to Group 3

** Visits only apply to group 3

*** These samples will only be collected if the participant has missed prior collection visit(s), in order to maintain the total number of biopsies indicated in the "Function" column.

Table 9-2 Mucosal biopsy collection schedule for Groups 4-5

Tissue	Function	Visit 4 (0 mo)	Visit 5 (1 mo)	Visit 9 (3 mo)	Visit 12 (4.5 mo)	Visit 14 (6 mo)	Visit 16** (9 mo)	Visit 17** (12 mo)

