For each tissue biopsy type, graphical and tabular summaries of the distributions of *ex vivo* inhibition of HIV-1 infectivity summarized by AUC (or other measurements) will be made for each challenge virus, treatment arm, and timepoint. Comparisons between groups 1-3 will be stratified by site. The difference between treatment arms at a specific timepoint will be tested with an extension of the nonparametric Wilcoxon rank sum test for two-way analysis (i.e., the Van Elteren test) if the data are not normally distributed and with a stratified 2-sample t-test if the data appear to be normally distributed. An appropriate data transformation may be applied to better satisfy assumptions of symmetry and homoscedasticity (constant variance). The same testing

approaches will be used to compare infectivity between male rectal vs. female cervical/vaginal, between male rectal vs. female rectal, and between female cervical vs. female vaginal at each time-point, stratified by dose groups.

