## 10. ASSAY SPECIFIC TABLES AND FIGURES FOR PROTOCOL TEAM REPORTS

### 10.1. Viral Infectivity (TLA)

### 10.1.1. List of Tables

- Summary statistics (i.e., min, mean, median, max, standard deviation) of  $AUC_{\text{day3-21}}$  by lab, sex at birth, tissue type, virus, visit, and treatment arm.
- Results of overall comparisons of  $AUC_{\text{day3-21}}$  at baseline between FH and CHIL lab using Van Elteren test, stratified by sex at birth, tissue type and virus combination.
- Results of overall comparisons of  $AUC_{\text{day3-21}}$  at baseline between female and male rectal samples using Van Elteren test, stratified by site and virus combination.
- Results of comparisons and correlations of  $AUC_{\text{day3-21}}$  at baseline between female cervical, vaginal and rectal samples, by lab and virus.
- Results of comparisons of  $AUC_{\text{day3-21}}$  between baseline and post-infusion visits, by tissue type, virus, and treatment arm
- Results of comparisons between treatment arms at baseline based on  $AUC_{\text{day3-21}}$  and at post-baseline visits based on baseline-subtracted or unsubtracted  $AUC_{\text{day3-21}}$ , by sex at birth, tissue type, virus, and visit.
- Results of comparisons between tissue types at baseline based on  $AUC_{\text{day3-21}}$  and at post-baseline visits based on baseline-subtracted or unsubtracted  $AUC_{\text{day3-21}}$ .

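### SAP 8.5.2 names only one rectal-versus-genital infectivity test, men's rectal against women's cervical/vaginal tissue, so it mixes tissue with sex although exploratory objective 4 is within participant

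*Protocol*

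**What the plan says.** Exploratory objective 4 (Protocol Section 5.3, repeated in SAP Section 3.3) is to compare levels and functionality "between the cervical, vaginal, and rectal compartments from the same participant".

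The tissue for this exists in some women. Protocol Section 4.4 lists "cervical and vaginal biopsies (as well as rectal secretions and biopsies at the Seattle site) in those born female" among the planned collections. Protocol Section 9.6 makes the rectal part voluntary: "At the Seattle CRS, female participants will also provide rectal fluids and rectal biopsies, if they agree to do so". Table 9-1 schedules infectivity biopsies from rectum and vagina together at Visits 2, 14, 15 and 16, and from cervix at Visits 2 and 14. The vaginal infectivity biopsies at Visit 17 are only make-up samples for missed visits.

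For the cross-tissue analysis, the plan in SAP Section 8.5.2 (Viral Infectivity) is this: "compare infectivity between male rectal vs. female cervical/vaginal, between male rectal vs. female rectal, and between female cervical vs. female vaginal". The timing and strata of these three contrasts are given as "at each time-point, stratified by dose groups". The method carried over from the treatment-arm comparison is this: "extension of the nonparametric Wilcoxon rank sum test for two-way analysis (i.e., the Van Elteren test) if the data are not normally distributed"; otherwise it is a stratified two-sample t-test. No paired method is named.

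The output lists add three relevant items:
- SAP Section 10.1.1 has a table of comparisons and correlations "at baseline between female cervical, vaginal and rectal samples, by lab and virus".
- The last bullet of SAP Section 10.1.1 is a table comparing tissue types at baseline and post-baseline, with or without baseline subtraction. It does not say which sexes enter or whether the data are paired.
- SAP Section 10.1.2 has scatterplots of women's rectal against cervical and rectal against vaginal AUC, by virus, visit and arm.

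**The concern.** Of the three contrasts named in SAP 8.5.2, only the first sets rectum against genital tract, and in it every rectal value comes from a man and every genital value from a woman. Sex cannot be used as a stratum because it coincides with tissue. A post-infusion difference may therefore reflect tissue, sex, or both.

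Two things are at stake. A reported rectal-genital difference in protection from ex vivo challenge could be partly or wholly a sex difference, or a real tissue difference could be masked by an opposing one. And the within-participant question, for which consenting Seattle women undergo biopsies of all three tissues, has no clearly specified post-infusion test.

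**Working it through.** **What each contrast estimates.** Write MR, FR and FG for mean infectivity in male rectal, female rectal and female genital tissue.

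FG − MR = (FG − FR) + (FR − MR)

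The named test targets the left side. The first term on the right is the within-woman tissue difference that objective 4 asks for. The second is the sex difference in rectal tissue.

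**No plan figure to reproduce.** The documents give no effect size, SD or power for a cross-tissue infectivity comparison. Protocol Table 6-3 concerns serum-mucosa correlation. It reproduces (n = 15, correlation 0.7: Φ[(0.867 + 0.025)·√12 − 1.96] = Φ(1.13) = 87%, as stated) but has no bearing here.

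**Inputs.** Groups 1 and 2 each enrol 10 men and 13 women (Protocol Section 6.1). Less the 15% allowed there for missing primary laboratory data, borrowed here for infectivity: 20 × 0.85 = 17 men and 26 × 0.85 = 22 women. Tests are two-sided at 0.05 (SAP 8.5.1). The sex differences, in SD units, and the within-woman correlation ρ are assumptions. Group 3 is left out.

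**Named contrast, no tissue effect, uncancelled sex difference d.** SE = √(1/17 + 1/22) = 0.323 SD. Rejection = Φ(d/SE − 1.96) + Φ(−d/SE − 1.96).

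| d (SD) | d/SE | Rejection |
|---|---|---|
| 0.3 | 0.93 | 15% |
| 0.5 | 1.55 | 34% |
| 0.8 | 2.48 | 70% |

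**Same question with the stratified rank test.** In 20,000 simulated trials of the Van Elteren test, with two dose strata of 8 men and 11 women, rejection was 5%, 11%, 30%, 57% and 81% for d = 0, 0.25, 0.5, 0.75 and 1. A paired t-test in women stayed at about 5% throughout. With a true tissue effect of 0.8 SD, the between-sex test rejected 62% of the time with no sex difference, but 14% or 96% with an opposing or reinforcing sex difference of 0.5 SD.

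**Price of pairing.** For k pairs, SE = √(2(1 − ρ)/k); the 95% half-width multiplies this by the t quantile on k − 1 degrees of freedom.

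| Comparison | SE (SD) | 95% half-width (SD) |
|---|---|---|
| Unpaired, 17 v 22 | 0.323 | 2.03 × 0.323 = 0.65 |
| Paired, k = 8, ρ = 0.5 | 0.354 | 2.36 × 0.354 = 0.84 |
| Paired, k = 12, ρ = 0.5 | 0.289 | 2.20 × 0.289 = 0.64 |

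About 12 pairs match the unpaired width at ρ = 0.5, and about 15 to 16 at ρ = 0.3. Simulated paired power for a 0.8 SD tissue effect, over ρ = 0.3 to 0.7, was 27–53% with 6 pairs, 48–83% with 10, 72–97% with 16 and 86–99.6% with 22.

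**The case against.** Much can fairly be said for the plan.

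- *A post-baseline comparison is listed.* A reader might infer that women's rectal tissue is never compared with their genital tissue after infusion. The documents do not support that: the last bullet of SAP 10.1.1 is not restricted by sex and could include it. But it states neither sex nor pairing, and the methods text that would define it omits the contrast.
- *The sex effect is examined.* A reader might infer that sex and tissue can never be told apart. Male against female rectal tissue is tested and estimates the second term of the identity above. This is a partial check: it covers rectal tissue only, relies on consenting Seattle women, and is not combined with the rectal-genital contrast. A non-significant result in a small set would not show that sex has no effect.
- *Baseline adjustment helps.* A reader might infer that it does not. Subtraction cancels an additive sex difference that is constant over time, and the rejection rates above then fall to about 5%. However, SAP 8.5.2 adjusts only if the Spearman correlation exceeds 0.5 with p < 0.05, and subtraction leaves any sex difference in post-infusion response.
- *The contrast is honestly named.* The SAP names both sexes and does not call it a pure tissue effect. That is true, but it is the only rectal-genital contrast named for an objective about compartments.
- *Pairs may be few.* Rectal biopsy of Seattle women is voluntary. A woman who switches from cervicovaginal to rectal sampling gives no pair thereafter, and rectal against cervical has one post-infusion visit. This stands, and is a reason to report the number of pairs.
- *The stakes are limited.* Objective 4 is exploratory, and secondary endpoint 1 does not depend on a cross-tissue contrast. This stands too.

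**Conclusion.** The point holds in a limited form. The only rectal-versus-genital infectivity test named in the SAP methods crosses the sexes and is unpaired, while the objective is within participant and some women supply the data for a paired answer. The same-woman comparison is specified only at baseline; after infusion it rests on an undefined table and scatterplots.

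The size is illustrative. Rejection of 15%, 34% or 70% with no tissue effect assumes sex differences of 0.3, 0.5 or 0.8 SD that baseline adjustment has not cancelled, 17 men and 22 women, and no dose stratification; the stratified rank test gives about 30% at 0.5 SD. The documents give no sex effect, SD, within-woman correlation or count of Seattle women with both tissues.

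Comparing standard errors alone, a reader might infer that about eight women would match the precision of the planned contrast. With t quantiles it is nearer 12 at correlation 0.5, and more at lower correlation. The case for pairing is that it removes the sex confounding and answers the stated objective, not that it is sure to be more precise. The change is worth making, for an exploratory objective.

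**What to change.** In SAP Section 8.5.2 and the last bullet of Section 10.1.1, specify the rectal-genital comparison as paired within women: signed-rank test, paired t-test, or a mixed model with a participant effect. Use AUC for Bal26, the only virus that SAP 8.5.2 applies to all three tissues. Compare rectal with vaginal tissue at Visits 2 and 14–16, and rectal with cervical tissue at Visits 2 and 14, among women with both tissues at the visit. Report the number of pairs at each visit.

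Keep male rectal against female cervical/vaginal tissue as a descriptive contrast, labelled as mixing sex and tissue.

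This changes SAP wording only and needs no new samples; SAP Section 1 provides for updating the plan before the final analysis. The downside is that fewer women contribute, so with fewer than about 12 pairs at correlation 0.5 the paired interval will be wider than the unpaired one.

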4.4.1 Dose and schedule

The proposed VRC01 doses for this mucosal study are based on doses that are being administered in the phase 2b efficacy trials, HVTN 703/HPTN 081 and HVTN 704/HPTN 085. As these doses (10 mg/kg and 30 mg/kg) are being evaluated on a large scale, interrogating the levels and functions of the antibody when administered at these same doses in serum, mucosal secretions, and mucosal tissues will be most informative and valuable for the field.

VRC01LS should have a longer half-life, therefore the dosing interval proposed is three months compared to a two-month interval with the VRC01 wild-type antibody. This interval is considered most likely to be utilized in a prevention effort and is also applied in the VRC 606 phase 1 study (Section 4.7.2). The 30 mg/kg VRC01LS dose also allows a direct comparison with the 30 mg/kg group of VRC01.

Groups 4 and 5, with a single infusion at 30 mg/kg will provide the opportunity to compare the PK profiles of the two antibodies in a more detailed manner.

VRC01 and VRC01LS are both formulated in vials at 100mg/ml (+/- 10mg/ml). Due to the concentration of the VRC01 antibody, large volumes are required for adult dosing and therefore IV administration will be used in this study.

